Data was not considered *sensitive* but the anonymity of participants needed to be protected (Gast & Ledford, 2014, p.43). Participant data was number-coded, so it could not be traced back to the participant's identifying information. The PI and rehabilitation manager were the only ones with access to the code, which was locked in a file cabinet in the speech therapy office. The number-code key will be shredded following completion of the research. No research data was entered into the participant's electronic medical record. Paper files of session data were also protected in the locked file cabinet. The investigation, participants, or participants' progress were not discussed with anyone not directly involved in the study, and for those involved communications were conducted in private locations, for example the speech therapy office. Any potential compromise of participant confidentiality was to be reported to the Internal Review Board (IRB) within one week; none occurred. Digital recording of every third session was used to obtain reliability and procedural fidelity data. Patient performance on the phrase completion task was videotaped every third visit/weekly using the hospital emergency iPad. The iPad was checked out in the morning before the participant's treatment session, the last treatment trial (for procedural fidelity) and the participant's pointing responses to the phrase completion task (for inter-observer reliability) recorded, and stored in the Speech Therapy office in the Rehabilitation building until viewed by the assistant in a private location and recorded on the paper reliability data forms. The digital recording was then deleted and the iPad returned. Digital videos did not show participants' faces, only hands circling the response were recorded.

Data storage included patient telephone numbers which were accessible in the participant's soft file for patient contact while the patient was undergoing speech therapy treatment, as is common practice. On discharge the soft file was stored in the Medical Records Department.

One potential problem would be a negative result, that music would decrease language/reading by overloading/interfering with semantic processing pathways used for language. Because progress was continually monitored, any negative result could be found quickly so severity and duration would be minimized, and intervention procedures adjusted to increase the potential for a

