3. A limited control set using listening to oral reading of the lyrics and silent reading of the written lyrics with observation of pointing to written lyrics (no music).

Dependent Variables:

The dependent variable was defined as silent reading/comprehension of targeted words/phrases by pointing to words/phrases in a phrase completion exercise without music. The dependent variable was kept constant for all three conditions.

Dependent Measures

Measurement of the dependent variable consisted of both direct systematic observational recording (DSOR) and treatment record video (for reliability/procedural fidelity assessment) of percentage correct over time (including follow-up) and trials- or sessions-to-criterion.

Research Design

An AATD was used for comparison of two separate but similar conditions when the effects may be non-reversible (see Gast & Ledford, 2014, pp. 324-332). Time between sessions was at least a day.

“Criteria:

1. Behaviors must be non-reversible—the behaviors will continue to be performed after instruction has stopped.
2. Behaviors should not be in the participants' repertoire.
3. Behaviors must be independent, meaning one behavior set/chain can be acquired without influencing performance on other behavior sets/chains.
4. Behaviors also must be functionally equivalent, meaning behaviors are likely to be influenced by the same environmental variable (e.g., the instructional strategies being studied).
5. *Behavior sets/chains must be of equal difficulty.* The dependent variable in this investigation will be phrases acquired, but three different sets will be required to fulfill the requirement that the behaviors are independent. To ensure that they are of equal difficulty, they must all be assessed for word complexity at a minimum.

Randomizing items between treatment conditions should result in a relatively equal distribution of difficulty” (Romer, Billingsley, & White (1988).

Procedures

All songs were pretested for familiarity and positive valence by questioning the participants (i.e. Do you know this song? Do you like it?). Response data was recorded. All songs perceived as not liked were eliminated and substitutions made; the new songs were then also pretested for familiarity and positive valence. Songs that were not familiar but were liked were noted but not changed.

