During the intervention (B), each song (music with lyrics) from set 1 (B1) was played in its entirety. When the targeted verse or chorus played, the written lyrics were simultaneously shown along with the song lyrics. The SLP pointed to the words of the targeted verse/chorus which was silently observed by the participant as they were sung. This was repeated for all ten songs. The phrase completion task was then presented, including the total 25 phrases, without music. The participant silently or orally read the phrase and circled the phrase completion choice. Correct responses were randomly verbally reinforced. Error responses were followed by verbal modeling and pointing to the correct choice by the SLP. The next session, each song (music with lyrics) from set 2 (B2) was played in its entirety. After the song played, the written lyrics from the targeted verse or chorus were presented. The SLP pointed to the words of the targeted verse/chorus which was silently observed by the participant. This was repeated for all ten songs. The phrase completion task was then presented, including the total 25 phrases. The participant silently or orally read the phrase and circled the phrase completion choice. Correct responses were randomly verbally reinforced. Error responses were followed by verbal modeling and pointing to the correct choice by the SLP. This was repeated for all ten songs. For all interventions, the number of correct responses were tallied on a LaPoint Base 10 form and the percent correct entered on the graph for that day. The same procedures were repeated, alternating procedures on sets 1 and 2 on subsequent treatment visits, until a criterion of 9/10 (90%) x 3 consecutive visits was reached on both sets. It was predetermined that if the criterion was not reached on one of the intervention sets, defined as no increase in percentage correct x 3 consecutive visits, that intervention would be considered to be limited in effectiveness and discontinued. Every third session was digitally recorded for a reliability check by the trained assistant. When both of the sets (B1 and B2) had been acquired or one acquired and the other discontinued, the number of sessions to criterion were counted for each intervention.

Potential Threats to Internal Validity

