Reliability of the items in the task assessment tool was established using Cronbach's Alpha correlation coefficient once at the beginning of the baseline phase. Inter-observer reliability on the scoring of the tool was determined weekly using the kappa coefficient, also known as Cohen's Kappa. Reliability data was first analyzed for normality/skewness, accuracy, and completeness. Outliers were identified using the Outlier Labeling Rule based on rank and percentile. If data were incomplete, for example if the behavior could not be clearly seen on the digital recording, the corresponding score from the other researcher was eliminated from the reliability determination.

The correlation coefficient chosen is dependent on the scale of measurement of the variables being correlated. For the reliability of the task assessment tool it was used to determine if scores recorded by one researcher were strongly correlated with scores recorded by the other. Scores were recorded as correct versus incorrect, which is a nominal scale. One classic correlation coefficient used with a nominal scale is Cronbach's Alpha, used when both X and Y are dichotomous variables. The assumption that the items of the test are unidimensional cannot be met, meaning that each item measures the same ability on the same scale, because many different mental processes may be used in various combinations from item to item. Cronbach's alpha provides a solution to this problem, so was an appropriate measure of internal consistency (Cronbach, 2004, see p.8). Acceptable values of alpha range from .70 to .90 (Tavakol &

Dennick, 2011). It was predetermined that if alpha was below .70, either the task assessment tool would be revised or the assistant would be re-instructed.

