- The difference in number of sessions/trials to achieve mastery at each level for each intervention, and the difference in retention at three weeks follow-up were analyzed by comparison of the difference between data points for the control treatment and the two target intervention conditions. After the research design has been completed by a minimum of four subjects, data will be consolidated for group means.

Data Storage

Patient telephone numbers were accessible in the participants' soft file for patient contact while the patient was undergoing speech therapy treatment, as is common practice. On discharge the soft file was stored in the hospital Medical Records Department.

Participants' performance on the phrase completion task was videotaped every third visit using the hospital emergency iPad. The iPad was checked out in the morning before the participant's treatment session. The last treatment trial (for procedural fidelity) and the participant's responses to the phrase completion task (for inter-observer reliability) were recorded and stored in the speech therapy office in the Rehab building until viewed by the assistant in a private location and recorded on the paper reliability data forms. The digital recording was then deleted and the iPad returned. Digital videos did not show participant faces, only hands on the response task were recorded.

Role of the researcher

The primary investigator (PI) pre-selected candidates for participation according to the stated recruitment procedures (above). The rehabilitation manager recruited participants, but the PI obtained informed consent. Given the therapy location, the PI conducted the experimental treatments, making adjustments to the protocol based on preliminary findings as necessary, with IRB approval for any changes. The PI was also responsible for training the (blinded) assistant for reliability checks from videotapes, and interpreting and reporting the data.

Assumptions and Limitations

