The role of the primary investigator presents the possibility of a threat to construct validity in the form of potential experimental bias, either by expectations of the subjects via the Hawthorne effect, or from unintentional experimenter effects. To reduce this threat, participants were blinded to the exact purpose of the experiment until all data was collected, and reliability checks of measurement data were conducted by an assistant blinded to the purpose of the study, but the study could still be limited by experimenter effects. Given a significant result of this investigation, follow-up systematic replication studies will be conducted in other locations with other skilled therapists performing the same experimental treatments.

Threats to internal validity included possible history or maturation effects. History effects are extraneous events prior to post-test that can affect the DV. Maturation effects are changes in the DV resulting from the passage of time, e.g. spontaneous recovery. In AATDs, a control set is used to rule out history and maturation effects.

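### In intervention sessions the second scorer works from video of a task in which the investigator gives unmasked feedback, so inter-observer agreement may be inflated and may miss scoring errors

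*Combined protocol and SAP*

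**What the plan says.** Procedures describes the scored task in intervention sessions: "The participant silently or orally read the phrase and circled the phrase completion choice". It then describes the feedback: "Correct responses were randomly verbally reinforced", and "Error responses were followed by verbal modeling and pointing to the correct choice by the SLP". Role of the researcher says that the investigator delivers the treatments, so this feedback is the investigator's own.

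Every third session is filmed, and the assistant fills in the reliability forms from the film. Data Storage states: "The last treatment trial (for procedural fidelity) and the participant's responses to the phrase completion task (for inter-observer reliability) were recorded". The confidentiality text under Human Rights Protections says that the film shows hands only and is deleted after viewing.

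Data Analysis adds two rules:
- When a response cannot be made out on the film, "the corresponding score from the other researcher was eliminated from the reliability determination".
- If agreement on any day is below 80%, or kappa squared is below .90, both researchers look at the recording again and try to reach consensus.

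Assumptions and Limitations cites the check as a protection against experimenter bias: "reliability checks of measurement data were conducted by an assistant blinded to the purpose of the study".

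The response mode is not described consistently. Procedures has the participant circle the choice. Dependent Variables defines the response as made "by pointing to words/phrases in a phrase completion exercise without music". Human Rights Protections refers in one sentence to "the participant's pointing responses to the phrase completion task (for inter-observer reliability) recorded" and in another to hands circling the answer.

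**The concern.** An inter-observer check is informative when the second score is formed without knowledge of the first. Here a correction after an item, or its absence, can tell the assistant how the investigator judged that item. Blinding to the study's purpose does not address this. No step mutes or cuts the film, or has the assistant score before the feedback.

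The investigator treats, runs the task, and interprets and reports the results. Of the two protections named in Assumptions and Limitations (participant blinding and this check), only the check bears on scoring. Single items matter: the mastery criterion is 9/10 on three consecutive visits, so one item separates 8/10 from 9/10 and can shift the count of sessions to criterion.

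A circled sheet would be a written record that can be scored without seeing the feedback. The plan does not use one for reliability, and once the film is deleted it cannot be audited later.

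**Working it through.** The plan reports no kappa, so there is no figure to reproduce. The checks below show how the plan's own rule behaves.

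**Inputs from the documents.** 25 items per session (Procedures); baseline errors 3 + 2 + 2 = 7 of 25, or 28% (Procedures), used as an illustrative error rate; acceptance at kappa squared of at least .90 (Data Analysis).

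**Assumed inputs.** m, the chance that each scorer independently mis-scores an item; c, the share of items on which the assistant simply follows the feedback.

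**Formula.** kappa = (po − pe)/(1 − pe), where po is observed agreement and pe is chance agreement from the margins. Tables are written (both correct; investigator correct only; assistant correct only; both incorrect).

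**1. What the rule demands.** Kappa squared of .90 means kappa of at least √0.90 = 0.949. One disagreement in 25 gives po = 0.96.
- (18, 0, 1, 6): pe = (18×19 + 7×6)/625 = 0.6144; kappa = 0.3456/0.3856 = 0.896; squared 0.80.
- (17, 1, 0, 7): pe = (18×17 + 7×8)/625 = 0.5792; kappa = 0.3808/0.4208 = 0.905; squared 0.82.
- Best case over all error counts, (12, 1, 0, 12): pe = 0.4992; kappa = 0.4608/0.5008 = 0.920; squared 0.847.

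So only perfect agreement on all 25 items passes, although 96% agreement clears the 80% limit easily.

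**2. One deletion.** If the single discordant item is dropped as not visible, agreement is 24/24 and kappa squared is 1.00 (provided that both correct and incorrect items remain; otherwise kappa is undefined). A fail becomes a pass.

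**3. Two investigator errors in 25, against an independent and accurate scorer** (po = 0.92).
- (19, 1, 1, 4): pe = 0.68; kappa = 0.24/0.32 = 0.750; squared 0.56.
- (19, 2, 0, 4): pe = 0.6768; kappa = 0.2432/0.3232 = 0.752; squared 0.57.
- (18, 2, 0, 5): pe = 0.632; kappa = 0.288/0.368 = 0.783; squared 0.61.

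A scorer who follows the feedback on every item gives 1.00.

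**4. Partial following.** With 28% errors, following the feedback on a share c changes kappa to 1 − (1 − c)(1 − kappa at c = 0). For m = 5%: po = 0.95² + 0.05² = 0.905; pe = 0.698² + 0.302² = 0.578; kappa = 0.775. At c = 0.5, kappa = 1 − 0.5×0.225 = 0.887.

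| m | kappa squared, c = 0 | c = 0.5 | c = 1 |
|---|---|---|---|
| 2% | 0.82 | 0.91 | 1.00 |
| 5% | 0.60 | 0.79 | 1.00 |
| 10% | 0.35 | 0.63 | 1.00 |

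**5. Deletion in general** (28% errors, m = 5%, c = 0; kappa squared 0.60 with nothing dropped).
- 10% of agreeing and 10% of disagreeing items dropped: 0.60.
- 10% of agreeing and 50% of disagreeing items dropped: 0.75.
- 10% of agreeing items only: 0.57.

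Deletion raises agreement only if the unseen items are more often discordant.

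**The case against.** Much of the case on the other side stands.

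- A reader might infer that agreement *is* inflated. The documents do not support that. They report no kappa and do not say whether the film has sound, whether the investigator's hand is in frame, or whether correction comes item by item or after the whole sheet.
- A reader might infer that the check *cannot* detect the investigator's errors. That goes too far. On an item-by-item reading the participant's choice comes before the correction, and the assistant is meant to score what is seen. A tally slip made after correct live feedback would still appear as a disagreement.
- Pairwise deletion is ordinary handling of a missing score, and nothing in the plan shows that unseen items are the contentious ones.
- The film includes a treatment trial that may show the music condition. The plan claims blinding only to purpose, so this breaks no stated masking.
- Error correction is described for intervention sessions only. At baseline, Procedures mentions praise for correct answers and for taking part, a weaker cue. No feedback is described at the retention test.
- Assumptions and Limitations does not present the check as the main safeguard. It admits that experimenter effects may remain and plans replication by other therapists if the result is significant.
- Multiple-choice items scored right or wrong leave little room for judgement.

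These points limit the claim but do not remove it: no step in the plan keeps the second score independent of the feedback.

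**Conclusion.** The point holds as a risk to the reliability evidence in intervention sessions. If the feedback is audible or in frame and given item by item, agreement may be inflated and investigator errors may be missed. The size cannot be derived from the documents. Under the assumed 28% error rate and 5% mis-scoring, following the feedback on half the items moves kappa squared from 0.60 to 0.79.

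The deletion rule adds to this only if unseen items are more often discordant. Because one disagreement in 25 already fails the .90 rule, a single such deletion can decide the result. The consensus review is a further route to high agreement if only the value after consensus is reported.

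A reader might go on to infer that the primary scores are wrong. Nothing in the documents shows that.

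**What to change.** 1. Reconcile circling (Procedures; one sentence of Human Rights Protections) with pointing (Dependent Variables; another sentence of Human Rights Protections), and state when feedback is given and what the film captures.
2. Where responses are circled, have the existing assistant score coded copies of the sheets against the key. Make the copies before the investigator adds any mark, and do this at least for the sessions now checked.
3. Where no usable sheet exists, have the assistant score film cut or muted so that the feedback is neither seen nor heard before the score is recorded.
4. Use the full film only for procedural fidelity, viewed after scoring.
5. Resolve items unclear on film from the sheet. Report the number still deleted, with a sensitivity figure that counts them as disagreements.
6. Report kappa before the consensus review, beside any later value.

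The cost is a change of wording, copying short forms and a little assistant time. Sample Size reports two participants against a minimum of four and a maximum of ten, so the change can apply to later participants. For the first two it is possible only if unmarked sheets were kept, which the documents do not say.

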During the baseline (A) all 25 phrases (Appendix C) were tested using the phrase completion task (Appendix D). Both correct responses and participation were verbally reinforced, as is required in an AATD. Results were analyzed by the SLP to ensure that the sets were of equal difficulty for each participant using two different procedures. First, logical analysis of the linguistic characteristics of the phrases was completed, including the number of words, the number of syllables in the words, the number of consonant blends in the words, and the number of contractions. Second, experimental evaluation of the number of error responses in each set during the baseline phase was completed, and without changing the items or responses, the set assignment was manipulated to maximally equate the number of error phrases without significantly changing the equivalency of the linguistic characteristics. One phrase was shifted from set 1 to set 2 during the baseline phase. In the end, the number of error responses on baseline for set 1 was three, for set 2 was two, and for the control set was two.

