Potential threats to internal validity included multiple-treatment interference in the form of sequential confounding and carryover effects. Counterbalancing conditions was necessary, and any carryover effects identified (see Gast & Ledford, 2014, chapter 5 p.101). Because AATD studies test efficiency, the goal involves demonstrating optimal performance as opposed to artificially deflated performance, so responses were reinforced during the baseline phase (see Gast & Ledford, 2014, p. 326).

Potential threats to internal validity also included possible history or maturation effects. A control set was used to rule out history and maturation effects.

Outcome Measures and Time Points

Pretest/post-test information on the ICF Body Functions/Structures, Activities, and Participation was provided (Hurkmans et al. 2011). The Boston Diagnostic Aphasia Examination (BDAE) (Goodglass, Harold, & Kaplan, 1983) was used as an outcome measure of reading acquisition. The BDAE is a classic anatomically-based diagnostic instrument. Because various components of language function may be selectively damaged by CNS lesions, results indicate the neuro-anatomical organization of language and localization of the lesion. Thus it serves as an appropriate assessment for research exploring neurological organization in the brain. Pretest reading scores on selected subtests from the BDAE full version were completed prior to baseline A and initiating intervention, and immediately following completion of intervention to assess generalization to non-trained stimuli. At four weeks follow-up the trained stimuli from all three interventions was retested to assess retention. The dependent variables, that is differential response to the two interventions (counted as the percent correct responses per day, a ratio scale which has equal intervals and an absolute zero, which allows for multiplication and division so is appropriate for averages), number of sessions required to achieve mastery at each level (simple counting but also a ratio scale as it has equal intervals and an absolute zero which allows for multiplication and division so allows for the difference between means), retention of the material (number of items remembered, another simple count which is also a ratio scale as it has equal intervals and an absolute zero and allows for the difference between means), was assessed using data analysis as described below.

Data Analysis

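### With two baseline-error phrases, a flat control set cannot exclude maturation within a single participant, although the plan says the control set rules it out

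*Combined protocol and SAP*

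**What the plan says.** In the combined protocol and SAP, Potential Threats to Internal Validity gives the control set its role: "A control set was used to rule out history and maturation effects". Assumptions and Limitations repeats it as a property of the design: "In AATDs, a control set is used to rule out history and maturation effects". The same paragraph gives spontaneous recovery as its example of maturation.

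Procedures reports the baseline result after the sets were balanced: "the number of error responses on baseline for set 1 was three, for set 2 was two, and for the control set was two". Treatment then continues "until a criterion of 9/10 (90%) x 3 consecutive visits was reached on both sets".

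For the control comparison, Data Analysis says only that differences between data points for the control and the two music conditions will be compared. It gives no test, margin or error rate. On pooling it says: "After the research design has been completed by a minimum of four subjects, data will be consolidated for group means". Sample Size requires at least four participants to show replication and says that this report covers the first two.

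**The concern.** A control set can reveal maturation only through items that have room to improve. Here there are two such phrases. If both stay wrong, the control set looks perfectly flat, yet two failures in two trials say little about the underlying recovery rate. Mastery of the music sets also requires few phrases to change, so a moderate recovery rate could meet the criterion with no effect of music.

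What is at stake is the attribution of a gain to music in participants recovering from stroke. If the control set is taken to rule out maturation, a flat control set in one participant would be read as settling a question that it cannot settle. This would be so even if the control phrases were never trained or corrected.

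**Working it through.** The plan gives no detectable change or error rate for the control set, so there is no figure of its own to reproduce.

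**Inputs from the documents**
- Baseline-error phrases: 3 in set 1, 2 in set 2, 2 in the control set (Procedures).
- Mastery: 9/10 on three consecutive visits, for both music sets (Procedures).
- Total phrases: 25 (Procedures).

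**Assumptions**
- Each music set has ten phrases. This is inferred from the ten songs and the 9/10 criterion, and leaves 25 − 20 = 5 control phrases. The results depend on the two control error phrases, not on the five.
- Each baseline-error phrase recovers independently with a common probability q. The documents give no value for q.
- A recovered phrase stays correct, in line with the non-reversibility criterion in Research Design. Phrases correct at baseline stay correct.

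**Phrases needed for mastery**
- Set 1 starts at 7/10 and needs 2 of 3 error phrases.
- Set 2 starts at 8/10 and needs 1 of 2.
- Bare mastery of both sets therefore needs 3 of 5.

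**What 0 of 2 excludes**
- The one-sided 95% upper limit for q is 1 − 0.05^(1/2) = 0.776.

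**Recovery alone, with no music effect**
- P(flat control) = (1 − q)².
- P(set 1 mastered) = 3q²(1 − q) + q³.
- P(set 2 mastered) = 1 − (1 − q)².

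| q | Flat control | Set 1 | Set 2 | Both sets | Both sets and flat control |
|---|---|---|---|---|---|
| 0.3 | 0.490 | 0.216 | 0.510 | 0.110 | 0.054 |
| 0.5 | 0.250 | 0.500 | 0.750 | 0.375 | 0.094 |
| 0.7 | 0.090 | 0.784 | 0.910 | 0.713 | 0.064 |
| 0.776 | 0.050 | 0.872 | 0.950 | 0.829 | 0.041 |

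The last column peaks at 0.094, near q = 0.52.

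**Direct comparison of music and control error phrases (Fisher exact, one-sided, control 0 of 2)**
- 3 of 5 recovered: C(5,3)/C(7,3) = 10/35 = 0.286.
- 4 of 5: C(5,4)/C(7,4) = 5/35 = 0.143.
- 5 of 5: C(5,5)/C(7,5) = 1/21 = 0.048.
- Set 1 alone at its best, 3 of 3: 1/C(5,3) = 1/10 = 0.10.

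**Pooling, if every participant had these counts and showed bare mastery with a flat control**

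Each stratum is then at its most extreme value given its total, so the stratified exact p is the product.
- Two participants: 0.286² = 0.082.
- Four participants: 0.286⁴ = 0.007.

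**Sensitivity of the peak joint probability (0.094 in the base case)**
- Sets of 9 and 11 after the shifted phrase: set 1 needs 3 of 3, and the peak falls to 0.030.
- Beta-binomial recovery with within-person correlation 0.3: 0.049. With correlation 0.8: 0.011.
- Responses independent from visit to visit: with the chance of a flat control over all visits held at 0.05 or 0.25, mastery of both sets by recovery alone has probability of about 0.001 or less over 6 or more visits.

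**The case against.** The strongest reply is that the two sentences state the purpose of a control set and do not say that a flat result in one participant proves anything. That is fair as to tone. But the plan supplies no other rule for reading the control set, and the stated purpose is one that two phrases cannot serve within a participant.

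A reader might infer that the control set is the only safeguard against spontaneous recovery. The documents do not support this. Sample Size and Data Analysis plan replication in at least four participants. Data Analysis also describes the slope in each phase, so a rising baseline could be seen. Neither measure rules out maturation within a participant, however. The two-standard-deviation band does not do so either, because it detects change from baseline whatever the cause.

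A reader might also infer that recovery alone fully accounts for mastery with a flat control set, or is its likely cause. The joint probability does not bear this out. It peaks at about 9% in one participant and at 0.094² = 0.9% if the pattern recurs in two participants with the same counts. It is lower still if phrases recover together, which is plausible for recovery affecting the whole person.

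Nor is it right that no result could separate music from control: 5 of 5 against 0 of 2 gives p = 0.048. The limit of p = 0.10 applies to set 1 taken alone.

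Finally, recovery shared by both music sets bears less on the set 1 versus set 2 comparison, which is a main aim of the design. That stands.

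**Conclusion.** The point holds for a single participant. A flat control set of two baseline-error phrases leaves recovery rates up to 77.6% unexcluded, and bare mastery of both music sets against it gives p = 0.286. Maturation is then not excluded, which is weaker than saying that it is probable.

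The result rests on ten phrases per music set, independent recovery at a common rate, and recovered phrases staying correct. Procedures gives one set of error counts without saying which participant they describe, so using them for every participant is a further assumption. Replication reduces the concern considerably by four participants, but at two the pooled p for bare mastery is still about 0.08. The claim affected is that music produced the gain.

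**What to change.** 1. In Potential Threats to Internal Validity and in Assumptions and Limitations, replace the claim that the control set is used to rule out history and maturation. Say that it gives limited evidence on maturation and cannot exclude it in a single participant with two control error phrases.
2. For each participant, report how many baseline-error control phrases became correct, with the exact one-sided 95% upper limit for that share.
3. In Data Analysis, base any maturation conclusion on a direct comparison of baseline-error phrases in the music sets with those in the control set. Use an exact test stratified by participant and pooled over participants. State that it assumes phrases are exchangeable across sets.
4. Do not declare maturation excluded merely because the upper limit lies below the share of phrases needed for mastery. With 0 of 8 over four participants the limit is 1 − 0.05^(1/8) = 31.2%, below the 50% needed in set 2. Yet recovery at that rate would still bring set 2 to 9/10 in 1 − (1 − 0.312)² = 53% of participants.

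The cost is wording and a small exact analysis. No new data are needed, because all 25 phrases are tested at each treatment session. The downside is that the report on the first two participants may not be able to claim that maturation was ruled out.
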